3. STUDY OBJECTIVES

The objective of this study will be to assess the efficacy and safety of Olumacostat Glasaretil Gel at a concentration of 5.0%, compared to Olumacostat Glasaretil Gel, Vehicle when applied twice daily for 12 weeks in subjects with acne vulgaris.

4. STUDY DESIGN

4.1 Overall Study Design

This study is a randomized, double-blind, vehicle-controlled, parallel group study, designed to assess the efficacy and safety of Olumacostat Glasaretil Gel, 5.0% compared to Olumacostat Glasaretil Gel, Vehicle in subjects with acne vulgaris on the face. All subjects will provide informed consent or assent (pediatric subjects) and undergo screening for study eligibility.

Approximately 700 eligible subjects \geq 9 years of age will be randomized, in a 2:1 fashion, to Olumacostat Glasaretil Gel, 5.0% or Olumacostat Glasaretil Gel, Vehicle treatment, respectively. Study drug will be applied twice daily to the face, and if applicable, to other affected areas on the chest, shoulders, and back, for 12 weeks. Subjects will return to the study clinic at Weeks 1, 4, 8 and 12 (Study Exit). A follow-up phone call at Week 2 will be made to assess safety (adverse events [AEs]) only.

Primary efficacy will be assessed through acne lesion counts (inflammatory and non-inflammatory lesions) and investigator global assessment of acne (IGA). All efficacy endpoints will be assessed as the change from Baseline to Week 12 on the face only.

Safety will be assessed through AEs, local skin reactions (LSRs), serum chemistry, hematology and urinalysis laboratory testing, electrocardiogram (ECG) testing, physical examination and vital signs.

4.1.1 Schedule of Visits and Assessments

The schedule of assessments can be found in Appendix 1 of the protocol.

4.1.2 Method of Assigning Subjects to Treatment Groups

A randomization schedule will be generated by a member of the Statistical Services department at QST Consultations, Ltd. (QST) who is not associated with the conduct or analysis of the study, using a validated system. The randomization list will not be stratified but stratification by site will be completed within the Interactive Web-based Randomization System (IWRS).

At the Baseline/Day 1 visit, qualified subjects will be randomized to treatment using the IWRS. The IWRS will assign a study drug kit number based on the subject's treatment assignment and available inventory at the investigational site. The kit number will be recorded in the electronic case report form. Approximately 467 subjects will be randomized to active treatment and approximately 233 subjects will be randomized to vehicle treatment for a total of approximately 700 subjects. Subjects will be randomized to treatment groups in such a manner to balance treatment allocation within study sites in a 2:1 fashion.

Statistical Analysis Plan for Dermira, Inc. Protocol Number: DRM01B-ACN03

4.1.3 Blinding

The Sponsor, the contract research organization, the investigator, study site personnel and subjects will be blinded to the treatment assignment. The randomization schedule will be kept strictly confidential and accessible only to authorized persons. Only when the study has been completed, the protocol violations determined and the study database locked will the randomization schedule be made available for analysis.

The integrity of this clinical study must be maintained by observing the treatment blind. If an AE occurs which cannot be managed without knowing whether the subject is receiving active study drug or vehicle solution, the IWRS will be used to obtain treatment assignment information. The Medical Monitor must be notified whenever study medication is unblinded, preferably prior to unblinding a subject.

4.2 Determination of Sample Size

The sample size for this study was based on estimates from the DRM01B-ACN02 study observed Week 12 results. Estimates were combined for all three active treatment groups as well as for the two vehicle groups. All power calculations were performed with nQuery Advisor Version 7.0 for a two-sided test at alpha = 0.05.

For inflammatory lesion change a sample size of 300 Olumacostat Glasaretil Gel and 150 Olumacostat Glasaretil Gel, Vehicle subjects has at least 95% power to detect a statistically significant difference with a significance level of 0.05 using the estimated absolute change from Baseline in treatment means of -15.21 and -9.7 for Olumacostat Glasaretil Gel versus its vehicle, respectively, with a standard deviation (SD) of 11.00.

For non-inflammatory lesion change a sample size of 450 Olumacostat Glasaretil Gel and 225 Olumacostat Glasaretil Gel, Vehicle subjects has 95% power to detect a statistically significant difference with a significance level of 0.05 using the estimated absolute change from Baseline in treatment means of -14.73 and -9.70 for Olumacostat Glasaretil Gel versus its vehicle, respectively, with a SD of 16.72.

The success rate for dichotomized IGA is estimated to be 20.5% in the Olumacostat Glasaretil Gel subjects and 9.6% in vehicle subjects. A sample size of 444 Olumacostat Glasaretil Gel and 222 Olumacostat Glasaretil Gel, Vehicle will have 95% power to detect a statistically significant difference in proportions of successes. These calculations were performed with nQuery Advisor Version 7.0 for a two-sided continuity corrected chi-square test at alpha = 0.05.

To allow for a slight loss in power due to dropouts and withdrawals as well as to accommodate sufficient power in all three co-primary variables, a sample of 700 subjects randomized to 2 to 1 for Olumacostat Glasaretil Gel (n=467) and vehicle (n=233), respectively, will be enrolled in the trial.

5. CHANGES IN THE CONDUCT OF THE STUDY OR PLANNED ANALYSES

There are no changes in the conduct of the study, but there are minor changes to the planned analyses.

The pooling analysis described in the protocol is updated in the statistical analysis plan (SAP) to reflect the intended analysis. The protocol discusses pooling sites with five or fewer subjects enrolled in each treatment arm. Taking into consideration the randomization ratio, the SAP requires ten subjects in the active treatment arm and five subjects in the vehicle group. The SAP also clarifies the pooling of sites will be performed for each country separately.

As part of the pooling analysis, the treatment effect within investigational site must be investigated. The protocol states the site main effect will be examined by using a one-way analysis of variance (for lesion count variables) or a logistic regression analysis (for dichotomized IGA) with a factor of site. The SAP instead explains site will be incorporated into the primary analysis models. Change from Baseline in lesion counts will be analyzed with an analysis of covariance (ANCOVA) (unranked or ranked) with factors of treatment group, investigational site and treatment group by investigational site interaction, and the respective baseline lesion count variable as a covariate. The dichotomized primary endpoint will be analyzed with a logistic regression with factors of treatment group, investigational site and the interaction term of treatment group by investigational site.

The protocol describes repeated measures sensitivity analyses for the primary efficacy endpoints. Treatment group, analysis center and visit are listed as factors for the repeated measures analyses. In addition to these factors, the SAP includes a factor of treatment group by visit interaction.

A subgroup summary of oral contraceptive used was added. Specifically, subjects will be categorized as Oral Contraceptives Approved for Acne Treatment Usage and No Oral Contraceptives Approved for Acne Treatment Usage.

6. EFFICACY AND SAFETY ENDPOINTS

6.1 Efficacy Endpoints

Primary and secondary efficacy endpoints will be assessed as the change from Baseline to Week 12 on the face only.

6.1.1 Primary Efficacy Endpoints

The primary efficacy endpoints are as follows:

 Mean absolute change in acne lesion counts (inflammatory and non-inflammatory lesions) from Baseline to Week 12; • Proportion of subjects who achieved ≥2-grade improvement and a grade of 0 or 1, in the IGA from Baseline to Week 12.

6.1.2 Secondary Efficacy Endpoints

The secondary efficacy endpoints are as follows:

- Percent change in acne lesion counts (inflammatory and non-inflammatory lesions) from Baseline to Week 12;
- Proportion of subjects who achieved ≥ 2-grade improvement in the IGA from Baseline to Week 12.

6.2 Safety Endpoints

Safety will be assessed through AEs, LSRs, serum chemistry, hematology and urinalysis laboratory testing, ECG testing, physical examination and vital signs.

7. STATISTICAL METHODS AND ANALYSIS

7.1 General Methodology

All analyses will be performed using SAS® Version 9.3 or later. No interim analyses are planned. Except where noted, all statistical tests will be two-sided and will be performed at the 0.05 level of significance.

Descriptive statistics will be used to provide an overview of the efficacy and safety results. For categorical parameters, the number and percentage of subjects in each category will be presented. For continuous parameters, descriptive statistics will include n (number of observations), mean, SD, median, minimum and maximum. Appropriate inferential statistics will be used for the primary, secondary and exploratory efficacy variables.

The primary method of handling missing efficacy data will be the method of Markov Chain Monte Carlo (MCMC) multiple imputation.

The primary method of dichotomizing the IGA score will be to consider a subject a "success" if the IGA at a post-baseline visit is 0 or 1 and 2 or more grades lower than at Baseline; otherwise the subject will be considered a treatment "failure".

Reported AEs, medical history terms, prior and concomitant procedures and therapies and washout procedures will be classified on the basis of Medical Dictionary for Regulatory Activities (MedDRA) terminology, Version 19.1. Prior and concomitant medications and washout medications will be classified on the basis of World Health Organization Drug Dictionary (WHO-DDE) terminology, Format B2, Version March 1, 2016.

7.2 Adjustments for Covariates

Baseline inflammatory lesion count will be a covariate for the primary efficacy endpoint for inflammatory acne lesion counts. Similarly, baseline non-inflammatory lesion count will be a covariate for the primary efficacy endpoint for non-inflammatory lesion counts. No other covariates are planned to be used in the analyses for this study.

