A similar procedure will be used for the analyses based on proportion of IGA successes wherein the ANCOVA analysis is replaced with a logistic regression analysis. Specifically, missing 12-week IGA values from which the dichotomized IGA is derived will be estimated by (MCMC) which does not rely on the assumption of data missing at random. Additionally, the pattern of missing observations in each treatment group cannot influence the missing value estimation in the other because the imputation is being conducted independently for each treatment group.

The missing 12-week IGA values will be derived for the analysis using the method of Markov Chain Monte Carlo (MCMC) multiple imputation. Multiple imputation and subsequent analysis will involve 4 principal tasks:

- 1. Calculate the number of missing values to be estimated by MCMC (nmiss) for 12-week value.
- 2. Create a data set, one for each treatment group, of subjects with observed values and those needing estimation by MCMC. The missing IGA values in each data set will be filled in using the MCMC method '5 x nmiss' times to generate '5 x nmiss' data sets. The resulting data sets for each treatment arm will be combined into one complete data set by imputation.

```
Syntax:
```

```
proc mi data=datain out=dataout seed=&seed. Nimpute=5xnmiss <options>; where trtpn=(TRT); /* Note TRT = [1, 2]; depending on treatment group */; mcmc chain=multiple; var baseline week4 week8 week12; run;
```

- 3. For each complete data set, the dichotomous success rate (clear or almost clear with a 2-point change from baseline) will be computed. The 12-week estimated global values will be rounded to the nearest integer value prior to evaluating the success rate. Each complete data set will be analyzed with a logistic regression with factors of treatment group and analysis center.
- 4. The results from these analyses will be combined into a single inference using SAS PROC MIANALYZE.

A total of 2 random seeds will be needed to impute IGA for the two treatment groups. Those 2 random seeds have been pre-specified by using a random number generator:

- IGA; Olumacostat Glasaretil Gel: Seed= 322979853
- IGA: Olumacostat Glasaretil Gel Vehicle: Seed= 1313477781

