- 2. Missing values will be filled in '5 x nmiss' times to generate '5 x nmiss' complete data sets. The imputation model used will be the analysis model.
- 3. For each complete data set, compute the necessary derived variables. Each complete data set will be analyzed with the appropriate analysis model. See Sections 7.3.2.1 and 7.3.2.2 for details.
- 4. Results from these analyses will be combined into a single inference using SAS PROC MIANALYZE.

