7.3.1.2 IGA Missing Data Imputation

A total of 2 random seeds will be needed to impute IGA for the two treatment groups. Those 2 random seeds have been pre-specified by using a random number generator:

- IGA; Olumacostat Glasaretil Gel, 5.0%: Seed= 322979853;
- IGA; Olumacostat Glasaretil Gel, Vehicle: Seed= 1313477781.

After imputing with PROC MCMC, the dichotomous success rate (clear or almost clear with at least a 2-point change from Baseline) will be computed. The 12-week estimated IGA values will be rounded to the nearest integer value prior to evaluating the success rate. Each complete data

set will be analyzed with a logistic regression with factors of treatment group and analysis center. The results from these analyses will be combined using SAS PROC MIANALYZE.

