7.3.2.2 IGA Missing Data Imputation

The first sensitivity analysis for the dichotomized IGA success will use a repeated measures logistic regression model (generalized estimating equations), with dichotomized IGA success as the dependent variable and treatment group, analysis center, visit (i.e., Week 4, Week 8) and treatment by visit interaction. In this analysis, data from all post-baseline visits will be included with no imputation for missing data.

The second sensitivity analysis will use the model-based multiple imputation method to impute missing data for the dichotomized IGA data at Week 12. The imputation model used will be a logistic regression with factors of treatment group and analysis center. One random seed will be needed to impute IGA for the two treatment groups. The random seed has been pre-specified by using a random number generator:

• IGA: Seed= 977235733.

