7.9.5 Demographic and Baseline Characteristics

All baseline summaries will be performed on the ITT, PP and safety populations.

Sex, race, ethnicity and Fitzpatrick skin type will be summarized by counts and percentages. Age will be summarized with descriptive statistics. Summaries of dichotomized age (less than median and greater than or equal to median) and categorized age (less than 18, 18 to less than median and greater than or equal to median) will also be included.

Subjects' baseline characteristics related to efficacy analyses will be summarized and compared between treatment groups to evaluate baseline balance between the treatment arms. Baseline inflammatory lesion count and baseline non-inflammatory lesion count will be compared using a two-way analysis of variance with factors of treatment group and analysis center. Baseline IGA will be compared using a Cochran-Mantel-Haenszel test of row means scores, stratified by analysis center.

Acne vulgaris history, including number of years since onset, anatomical areas affected and prior acne treatments, will be summarized by counts and percentages. If only the year is known for start of acne vulgaris the number of years since onset will be calculated by using January for

month and "01" as day. If only the year and month are known for start of acne vulgaris then onset will be calculated by using "01" as day.

Medical histories will be coded using the MedDRA dictionary and presented in a by-subject listing.

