Note that interaction and skewness p-values will be computed for each imputation of multiply-imputed data. Model determination will depend on averaged p-values, computed by finding the mean p-values across all imputations.

The proportion of subjects who are dichotomized to success at Week 12 will be analyzed using a logistic regression with factors of treatment group and analysis center.

The sensitivity analysis for absolute change in lesion count will include a skewness test, based on the methods presented by J.H. Zar (1984) [1]. A ranked repeated measures analysis of covariance with factors of treatment group, visit, analysis center and treatment by visit interaction, and the respective baseline lesion count as covariate will also be included. Values will be ranked across all visits (i.e. visit will be ingored when ranking) and the baseline covariate will not be ranked.

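### The primary IGA model leaves out baseline IGA grade, although both lesion-count co-primaries adjust for their own baseline (low-priority improvement, not an error)

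*SAP*

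**What the plan says.** SAP 7.2 names two covariates, the baseline inflammatory and baseline non-inflammatory counts, each for its own endpoint, and closes with "No other covariates are planned to be used in the analyses for this study".

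For the IGA co-primary, SAP 7.9.7.1 says that the proportion of successes "will be analyzed using a logistic regression with factors of treatment group and analysis center". SAP 7.3.1.2 applies the same model to each imputed data set, and Protocol 11.3 and 11.7 agree.

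Of the two IGA sensitivity analyses in SAP 7.3.2.2, the GEE model has treatment, center, visit and treatment by visit. For the model-based imputation, "The imputation model used will be a logistic regression with factors of treatment group and analysis center". SAP 7.3 ties the two models together: "The imputation model used will be the analysis model".

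Baseline IGA is used in three other places:
- the variable list of the primary MCMC imputation (Protocol 11.7: "depending on treatment group */; mcmc chain=multiple; var baseline week4 week8 week12; run");
- the balance check in SAP 7.9.5 ("Baseline IGA will be compared using a Cochran-Mantel-Haenszel test of row means scores, stratified by analysis center");
- a descriptive subgroup of grade 3 and grade 4 (SAP 7.7).

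Randomization is stratified by site only (SAP 4.1.2).

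**The concern.** One co-primary of three is not adjusted for its own baseline, and the SAP gives no reason. Entry requires grade 3 or more on a scale that ends at 4 (Protocol 5.3.1 and 9.2.1), and success means grade 0 or 1. A grade 3 subject must therefore drop at least two grades and a grade 4 subject at least three. Baseline grade is likely to predict success, although the documents do not say how strongly.

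Two things would be lost. The first is a little precision. The second is a pre-specified correction for chance imbalance in severity. The balance test and the subgroup table can reveal an imbalance but do not correct the primary result, and a covariate added after seeing one would be post hoc.

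**Working it through.** **Inputs.** From SAP 4.2: success 20.5% active and 9.6% vehicle; two-sided alpha 0.05; continuity-corrected chi-square; 444 and 222 subjects for 95% power; 467 and 233 enrolled. Assumed, because the documents give neither: grade 4 share s of 10-30%; odds ratio of success, grade 4 vs 3, of 0.2-0.4, the same in both arms.

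**1. The plan's own figure.** Power = Φ[(d − c − 1.96·SE0)/SE1], where d = 0.205 − 0.096 = 0.109, c = ½(1/n_v + 1/n_a), SE0 is the pooled and SE1 the unpooled standard error.
- 444 and 222: c = 0.00338, SE0 = 0.03078, SE1 = 0.02753. (0.109 − 0.00338 − 0.06033)/0.02753 = 1.645, so power is 95.0%, as stated.
- 467 and 233: c = 0.00322, SE0 = 0.03004, SE1 = 0.02686. The ratio is 1.746, so power is 96.0%.

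The sizing never used a baseline covariate, so the omission changes no stated figure.

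**2. Asymptotic gain, centers ignored, 467 and 233.** Without grade: log OR = ln(0.205/0.795) − ln(0.096/0.904) = 0.887; SE = √[1/(233 × 0.096 × 0.904) + 1/(467 × 0.205 × 0.795)] = 0.2502; z = 3.546; power = Φ(3.546 − 1.96) = 94.4%. With grade, intercepts were solved so that the arm rates stay at 20.5% and 9.6%, and the SE came from the expected information. The ends of the assumed grid are:

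| Grade 4 share | Grade odds ratio | Conditional treatment OR | SE | z | Power |
|---|---|---|---|---|---|
| 10% | 0.4 | 2.44 | 0.2508 | 3.557 | 94.5% |
| 30% | 0.2 | 2.51 | 0.2540 | 3.620 | 95.2% |

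The gain is 0.1 to 0.8 points. The marginal odds ratio is 2.43.

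**3. Simulation with centers as fixed effects.** 700 subjects, about 2:1 within each of 25 or 45 equal centers (SAP 7.5 sets a minimum of 15 per center, and 700/15 allows at most 46), center SD 0.4 on the logit scale, centers without successes dropped. The (share, odds ratio) pairs were (0.1, 0.4), (0.2, 0.3) and (0.3, 0.2). Both models were fitted to the same trials: 24,000 (25 centers) and 10,000 (45 centers) per pair under the null, 16,000 and 8,000 under the alternative.

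| Centers | Null rejection, center only | Null rejection, plus IGA | Power, center only → plus IGA |
|---|---|---|---|
| 25 | 5.2-5.5% | 5.2-5.5% | 96.96 → 97.10; 97.08 → 97.28; 96.99 → 97.31 |
| 45 | 5.3-5.8% | 5.4-5.9% | 97.54 → 97.62; 97.70 → 97.76; 97.58 → 98.11 |

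The gain is 0.1 to 0.5 points (paired SE 0.06-0.12), or 0.0 to 0.3 points with cut-offs corrected to true 5% size. Adding the factor raises null rejection by 0.0 to 0.3 points (SE 0.06-0.15), which is no clear inflation. Power levels here are not comparable with step 2, which is a normal approximation; only the differences within each step are.

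**4. Chance imbalance.** SD of the difference in grade 4 share = √[s(1 − s)(1/467 + 1/233)] = 2.4 points at s = 10% and 3.7 at 30%. Take a 1.96-SD difference D with the pooled share held fixed. The crude difference moves by D × [(233/700) × active gap + (467/700) × vehicle gap], where a gap is the success rate in grade 3 minus that in grade 4.
- s = 10%, odds ratio 0.4: 4.72 × (0.333 × 11.7 + 0.667 × 5.9)/100 = 0.4 points.
- s = 30%, odds ratio 0.2: 7.20 × (0.333 × 19.7 + 0.667 × 9.7)/100 = 0.9 points.

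Simulated power over the three pairs (no centers, 20,000 trials each):

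| Imbalance of 1.96 SD | Crude | Adjusted |
|---|---|---|
| Against active | 93.7-95.7% | 97.0-97.6% |
| In favour of active | 97.9-98.8% | 96.9-97.1% |

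**5. Model-based sensitivity imputation.** The bias from leaving grade out is the missing fraction × the grade 4 excess among the missing × the gap. It is zero if the missing subjects have the completers' grade mix. With 10% missing and a 20-point excess in the active arm only, it is 0.10 × 0.20 × 11.7 to 19.7 = 0.23 to 0.39 points. If both arms are affected, it is 0.12 to 0.20. With 5% missing and a 10-point excess in the active arm, it is at most 0.10. These are formula results; missing data were not simulated.

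**The case against.** The strongest reply is that nothing is broken. The model is pre-specified, identical in protocol and SAP, and valid because treatment is randomized. Size-corrected, the gain is 0.0 to 0.3 points on power of about 97-98%. The imbalance shift of 0.4-0.9 points is only 0.14-0.35 of the 2.7-point standard error of the crude difference, and an imbalance in active's favour is as likely, in which case adjustment costs 1.0-1.7 points of power. All of this stands, and it is why the item ranks low. The last point is not a defect of adjustment, though: it removes an advantage that arose by chance.

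It also stands that every size depends on assumptions (grade 4 share, prognostic strength, center SD, equal centers), and that the imbalance figures leave out centers. Over a wider assumed grid (share 10-40%, odds ratio 0.1-0.5) the asymptotic gain is 0.1 to 1.6 points. If grade is not prognostic, nothing is gained.

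SAP 7.2 alone is imperfect evidence, since analysis center is in the models as a factor although 7.2 does not list it as a covariate. The model statements in SAP 7.3.1.2 and 7.9.7.1 settle the matter.

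Finally, at a 10% share only 0.5-1.0 vehicle successes are expected in grade 4, so the grade coefficient would be imprecise. It is one coefficient shared by both arms, however, and the null rejection rates show no harm.

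**Conclusion.** The point holds as a low-priority improvement. Baseline IGA is absent from the primary IGA model and from both IGA sensitivity models, with no reason given, while the other two co-primaries adjust for their own baseline. Type I error and the stated power are not in question.

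Under the assumed range, the average power gain is a fraction of a point. The main benefit is that power stays near 97% whichever way a marked severity imbalance falls, where the crude test runs from 93.7% to 98.8%. That, and consistency across the co-primaries, is the case for the change.

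**What to change.** Before unblinding:
- Add baseline IGA (3 vs 4) as a factor in the primary IGA logistic model: SAP 7.2, 7.3.1.2 and 7.9.7.1.
- Add it to the GEE model and the model-based imputation in SAP 7.3.2.2. The imputation has to follow, because SAP 7.3 equates it with the analysis model. The primary MCMC imputation already includes baseline grade.
- Keep the treatment-plus-center model as a sensitivity analysis, and record the change in SAP Section 5.
- State that the odds ratio is conditional on baseline grade, and also report a marginal (standardised) risk difference.
- In SAP 7.9.7.2, which reuses the primary logistic method, state whether the factor applies to the 2-grade endpoint. This is optional, and no gain is claimed for it.

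If the sponsor prefers the present model, one sentence in SAP 7.2 explaining why IGA is treated differently would do.

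The cost is text edits and one extra table, with no new data, visits or subjects. It does change a co-primary model on which protocol and SAP now agree, so the Section 5 entry is needed. The SAP should also say plainly which of the two models is primary, in case they disagree near 0.05.
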